#### **Concomitant medications**

All prescription medications taken within 30 days of study screening will be recorded. Medication known to influence CNS-activity will be assessed for each patient. Subjects will be allowed to participate when they have been on a stable dose for at least 3 months prior to the first study day. Medications with a strong influence on CYP3A4 metabolism are an exclusion criterion.

#### Tolerability / safety endpoints

- Adverse events
- Vital signs measurements
- General physical examination findings (only performed when clinically indicated)

#### Pharmacokinetic endpoints

Part A: serum and saliva. Part B: saliva only.

- The maximum serum concentration, Cmax
- The time to reach maximum serum concentration, tmax
- The terminal disposition rate constant ( $\lambda z$ ) with the respective half-life, t/2
- The area under the serum concentration-time curve from zero to infinity, AUC0-inf
- The area under the serum concentration-time curve from zero to t of the last measured concentration above the limit of quantification, AUC0-last
- Clearance, Cl
- Volume of distribution, Vz

#### Trial@home endpoints

- Physical activity
- Sleep (duration, %light sleep, amount of times woken up)
- Heart rate
- Daily symptom scores
- Tapping frequency, adaptive tracking, animal fluency (twice-weekly)

#### Pharmacodynamic endpoints

- NeuroCart
  - Adaptive Tracking
  - o Animal fluency test
  - o Body Sway

- Saccadic Eye Movements
- Smooth Pursuit Eye Movements
- Tapping frequency

#### • Questionnaires

- o ABC (Aberrant Behaviour Checklist) questionnaire (parents, teacher)
- Clinician's Global Impression of Improvement and Severity (CGI-I, CGI-S)

#### Sample Size Justification and statistical methodology

For part A, Linear and non-linear relationships between plasma and saliva concentrations will be explored. In the case of a nonlinear relationship, which could be expected due to delayed penetration in the salivary compartment, it is widely accepted that around 20 subjects are necessary to develop a reliable model. The predictive capability of the two regression equations will be compared to determine which method is superior.

For part B, the sample size is based on practical considerations (the total ARID1B population in the Netherlands) and based on the previous study (CHDR1828). We consider 20 patients to be a feasible amount of subjects to recruit, while obtaining sufficient power to detect clinically relevant treatment effects. To establish treatment effects the repeatedly measured cross-over PD endpoints will be analyzed by mixed model analyses of variance with treatment, period, time, and treatment by time as fixed effects, with subject, subject by treatment and subject by time as random effect, and with the (average) baseline value as covariate. The PK-PD relationship between clonazepam concentration and PD endpoints will be assessed by calculating the estimated plasma concentration using the derived formula in part A of the study.

#### TABLE 1. ASSESSMENT SCHEDULE PART A (HEALTHY VOLUNTEERS)

	SCR	Study day									
Time Assessments	-28 days	-1 h	0 h	0.5h	1h	2h	4h	6h	8h	24h	48h
Informed consent	Х										
Demography	Х										
Inclusion and exclusion criteria	Х										
Medical history	Х										
Height / weight	Х										
Blood chemistry, coagulation, hematology and virology	Х										
Alcohol breath test	Х										
Urine drug screening, urinalysis	Х										
Urine pregnancy (females)	Х										
Vital signs (HR, BP)	Х	Х									
Vital signs (temp)		Х								Х	Х
COVID-19-related questions		Х								Х	Х
Symptoms	Х	Х			Х		Х		Х	Х	Х
Arrival in clinic		Х								Х	Х
Drug administration (oral)			Х								
Rinse mouth			Х	Х	Х	Х	Х	Х	Х	Х	Х
Blood and Saliva sample PK			Х	Х	Х	Х	Х	Х	Х	Х	Х
Discharge		1							Х	Х	Х

SCR = screening; BS = blood sample; PK = pharmacokinetic; HR = Heart rate; BP = Blood pressure

## TABLE 2. ASSESSMENT SCHEDULE PARTS B (ARID1B SUBJECTS)

	SCR		Study period 1 & 2					
			Day 1 & 22				Day 2- 21	
Time	-60 days 	-1 h	0 h	1h	3h	4.5h	5h	
Informed consent	Х							
Demography	Х							
Inclusion and exclusion criteria	Х							
Medical history	Х							
Symptoms	Х	Х	Х	Х	Х		Х	
Arrival in clinic		Х						
Explanation of NeuroCart® and study procedures	Х	х						
Vital signs (Weight, length, HR, BP & temp)		х						
Adverse events			Х	Х	Х		Х	X7
Questionnaires 		Х						
Drug administration (oral)			Х					X 
Cognitive test battery 		Х		Х	Х		Х	
Rinse mouth		Х				Х	Х	
Saliva sample PK		X6				Х	Х	
Discharge							Х	
trial@home device explanation to parents							Х	
trial@home 			Ī	Ì				Х
Teacher/caregiver questionnaire								X 

SCR = screening; PK = pharmacokinetic; HR = Heart rate; BP = Blood pressure

1. Questionnaires consists of: ABC questionnaire, and the Clinician's Global Impression (CGI-S at day 1, CGI-I at day 22).

2. Continuous physical activity, heart rate and sleep monitoring, as well as twice-weekly finger tapping, adaptive tracking and animal fluency.

3. NeuroCart tests consist of: animal fluency test, adaptive tracking, body sway, saccadic eye movements, smooth pursuit and tapping frequency.

4. Screening by phone.

5. ABC questionnaire on paper. Interview by phone for CGI-S (> day 1) and CGI-I (> day 21), conducted as soon as possible after the study-day.

6. Only on day 22

7. Evaluation adverse events by phone by study physician at Day 3 and Day 6 and when needed

8. Starting on the evening of Day 22, clonazepam will be tapered by decreasing the daily dose by 0.01 mg/kg/day every three days.

## 1 BACKGROUND AND RATIONALE

## 1.1 Context

Intellectual disability (ID) is one of the most frequent neurodevelopmental disorders and affects up to 2-3% of the population [1, 2]. Large-scale genetic studies have shown that in many patients with ID genetic causes can be identified [3, 17]. Heterozygous truncating mutations in ARID1B, leading to haploinsufficiency, are continuously found as the most frequent cause of ID, explaining about 1% of the patients [3, 4]. Besides non-specific ID, ARID1B mutations have been identified in a high proportion (>50%) of patients with a clinical diagnosis of Coffin-Siris syndrome [5-7]. This syndrome was first described in 1970 as a combination of course facial features, hypertrichosis, and fifth digit nail hypoplasia. Other symptoms that have been reported are epilepsy, feeding disorders, congenital heart disease, speech impairment and agenesis of the corpus callosum [8, 9]. Almost all adults with ARID1B mutations are incapacitated. Although there are no good estimates of incidence and prevalence, ~50 patients with ARID1B mutations are currently known in the LUMC's expertise center. Worldwide the largest group of described patients consists of 143, reflecting the accessibility of clinical genetics in the Netherlands. Currently, no treatment options are available for ARID1B patients, except for supporting therapies such as physiotherapy and speech therapy.

There is little knowledge on the pathophysiology of ARID1B mutations. However, ARID1B is one of the members of a chromatin remodeling complex (BAF complex). The subunit composition of this complex plays a key role in neural differentiation. Since mutations in other components of the BAF complex have also been identified in Coffin-Siris syndrome, it is likely that these mutations lead to impaired neural differentiation and ID.

In the past two years three Arid1b-haploinsufficient (Arid1b+/-) mice models have been generated and investigated. Although different tests have been performed in these studies, and results are not always in agreement, the emerging picture is that Arid1b+/- mice display increased anxiety, reduced memory, learning and social interaction [12]. One study identified growth hormone (GH) deficiency in Arid1b+/- mice, and showed that GH treatment does not have an effect on behavioral tests. Interestingly however, ARID1B patients are shorter than their sibs, and GH deficiency has been observed in patients, indicating that the mouse model does have validity.

In another study mouse brain tissue was extensively investigated, and the amount of GABAergic inhibitory interneurons, especially of the parvalbumin-positive subtype, was reduced. This prompted investigation of the ratio of inhibitory and excitatory synapses, which indeed showed a reduction of GABAergic inhibitory synapses. Further analysis showed increased apoptosis in the progenitor population in the medial ganglionic eminence, which is the likely cause of the reduced numbers of inhibitory interneurons since it is the origin of 60-80% of cortical interneurons.

Based on these findings, the investigators decided to administer a single treatment of 0.0625 mg/kg i.p. clonazepam in adult mice. This treatment led to restored impaired recognition memory, social memory and heightened anxiety-like behavior in adult Arid1b heterozygous mice, but not depression-like behavior symptoms 30-60 min after treatment [11].

Currently, this is the only study to directly implicate a key role of GABAergic interneurons in ARID1B pathophysiology. However, the GABAergic system has been previously linked to various other syndromes which feature ID, such as Fragile-X, Rett, and Down syndromes. To provide further support for the involvement of the GABAergic system, the Leiden University Medical Center has generated ARID1B haploinsufficient (ARID1B+/-) and ARID1B knockout (ARID1B-/-) induced

pluripotent stem cells by using CRISPR-Cas technology. Upon differentiation to GABAergic interneurons, we noticed that the cell number sharply decreased with decreasing functioning copies of ARID1B.

Together, this data leads to the hypothesis that haploinsufficiency of ARID1B leads to fewer interneuron progenitors and GABAergic inhibitory interneurons, and an imbalance in excitatory/inhibitory synapses, whilst providing stimulation to the GABAergic system restores this balance and at least partially restores the consequences on behaviour and cognition.

## 1.2 Endpoints and biomarkers in ID.

Thus far, no detailed characterization of ARID1B patients has been performed, and there are no widely accepted biomarkers in ID. For an extensive discussion on biomarkers we refer to Cohen *et al.* [18]. Ideally, a biomarker shows a clear difference between patients and controls, has little withinpatient variability, correlates well to a relevant endpoint, and reflects treatment response. Since no treatment is currently available, the last criterion cannot be established. Therefore, Centre for Human Drug Research recently performed a first exploratory study to investigate the neurocognitive phenotype in 12 ARID1B patients aged 2-31 years and 12 age-matched controls. Patients and controls had 2 visits at the CHDR, and all measurements were performed 2-4 times. The goals of this study were to (1) establish which tests could be performed by ARID1B patients, (2) the variability of these tests within each patient, (3) the variability of the tests between patients, and (4) the difference between patients and age-matched controls. Based on previous experience and literature we selected a subset of tests of the NeuroCart® (CHDR1828).

Important results of these study were that the vast majority of the tests could be performed adequately by ARID1B patients. The burden (2x 3h visits) to the patients was acceptable, given that most patients indicated they would consider participating in future studies. We did notice however that especially EEG-related tests were difficult to perform, and that the placement of EEG caps was a lengthy and burdensome process in the patient population.

Analysis of the results focused on desirable characteristics for biomarkers for future trials, such as a clear difference between patients and controls, and limited variability within and between patients. Several tests satisfied these criteria, most notably adaptive tracking, smooth pursuit, body sway, tapping frequency, and the animal fluency test. We have also correlated these markers to disease severity as measured by IQ and the Aberrant Behavior Checklist, but the small sample size does not allow definitive conclusions.

Most of these biomarkers have previously been evaluated in benzodiazepines. Sedative effects of benzodiazepines can be readily identified by their effect on saccadic eye movements. As expected, CHD1828 did not identify any differences between ARID1B patients and controls in saccadic eye movement.

Another important aspect of biomarker selection is whether they could potentially be measured in the home environment. Since ARID1B syndrome is a rare disease, patients have to come from all over the country. Especially for multiple dose studies, measuring endpoints in the home environment offers substantial advantages. CHDR has developed a trial@home platform called CHDR MORE®. It offers multiple study assessments for use in a home-setting. It includes a wearable platform using devices produced by Withings, such as the Withings Steel HR, a smartwatch capable of measuring physical activity, heart rate and sleep characteristics. Furthermore, the platform consists of the Promasys

ePRO application, enabling study participants to answer digital questionnaires and allowing investigators to send phone notifications when it is time for a study assessment.

#### 1.4 Study rationale

#### 1.4.1 Benefit and risk assessment

This is an interventional trial with the aim of benefiting patients. The NeuroCart® assessments have been previously evaluated in the study population (study CHDR1828). The measurements were well tolerated, and most patients indicated they would consider participating again in a trial when asked. The most disliked assessment (EEG measurements) are not included in this trial. Therefore, we estimate the assessment burden for subjects is relatively lower than during CHDR1828.

The actual burden for subjects consists of the time spend at CHDR and the potential side-effects from clonazepam treatment. The 4 study days will last approximately 6.5 hours, but include 5 hours of break time. In this time, subjects can roam freely and sufficient entertainment will be arranged together with parents. The study does not include blood draws or other invasive measurements. Clonazepam is a registered drug and approved for use in pediatric patients. Possible adverse events include fatigue, diminished concentration, dizziness and headache. Furthermore, extremely rare paradoxal reactions have been reported: irritability, aggression, agitation, nervousness, hostility, anxiety, sleep disturbances, nightmares, abnormal dreams, hallucinations. Patients will be monitored during each study day and the investigator will be continuously available for parents and caregivers. Dose-adjustment or study discontinuation will follow in the case of clinically relevant adverse events.

Study subjects will have potential benefit from study participation. Pre-clinical data suggests an effect on behavior and cognition. The additional value of this research is in gaining the first insights into the neurocognitive effects of clonazepam treatment on ARID1B-related ID subjects and possible validation of novel noninvasive endpoints obtained via the NeuroCart®. The proposed research can be considered group-related because it is only feasible by including ARID1B-related ID patients themselves.

## 1.4.2 Medical and regulatory background

The investigator will follow the code of conduct 'The expression of objection by people with mental disabilities in the context of the WMO', originally published as TVAZ 17: 3, 1999, and the code of conduct regarding conducting research with minors ('Gedragscode bij verzet van minderjarigen die deelnemen aan medisch wetenschappelijk'onderzoek'). If a patient objects to the Neurocart® tests, the test will be skipped and a 10-minute break will be provided before the subject will conduct the next test. If the patient still objects no further tests will be performed and the patient will either drop out of the study or continue the study at the next study day, depending on the amount of completed tests and the opinion of parents and caregivers. Objection of the patient will be interpreted considering the usual behavioural pattern of the patient. As the parents and caregivers are best informed about the usual behaviour of the patient, they will be mostly responsible to decide whether or not the patient objects.

## 1.4.3 Study population

This research can only be carried out in ARID1B patients. Based on the results of our exploratory study (CHDR1828) we have chosen to include patients aged 6 and older, since these children were able to execute the NeuroCart®-related tasks. Considering the rarity of the disease, it is not possible to conduct the complete study in a subgroup, e.g. relatively competent or adult patients. All adults known to date are incapacitated. In addition, based on the hypothesized mechanism of action and brain plasticity it is possible that the treatment will only work in younger children. However, we will start this study with a cohort of 5 subjects aged 12+.

## 1.4.4 Study design

**Rationale for part A (healthy volunteer study).** Clonazepam PK is variable due to variations in CYP3A4 activity. Although plasma sampling is not desirable in the ARID1B patient population, knowledge of PK is required to establish concentration-effect relationship and the development of PK/PD models. Therefore, we will first conduct a limited study in healthy volunteers where plasma PK and saliva PK are correlated.

De Gier et al show that there is a close correlation between salivary and plasma levels of diazepam [19]. In a similar study Hallstrom et al confirmed this correlation although the correlation coefficient was lower (0.81 versus 0.96) [20]. No plasma-saliva PK studies have been performed with clonazepam, but urine and saliva PK has been investigated in subjects undergoing withdrawal which show that clonazepam detection in saliva is extremely sensitive [21]. Considering the nature of this part of the study, we will only include healthy adult volunteers.

**Rationale for part B (cross-over study).** Since the ARID1B patient population is small, with significant variability between patients, but limited within patients as demonstrated by our study CHDR1828, and the disease itself is stable, a cross-over design has been selected for the current study. In order to establish the acute and chronic administration of clonazepam whilst taking into account the development of tolerance to some of the effects of benzodiazepines, there is a 3-week treatment period with detailed measurements on the first and last days. By combining measurement of biomarkers with clinically relevant endpoints (such as cognition and behaviour) we can establish clonazepam effect on both, and test whether responses to acute and chronic treatment correlate.

## 1.4.5 Comparative drug(s) and/or placebo

Since there is currently no approved or effective pharmacological treatment available for ARID1B related intellectual disability, the choice was made for a placebo-controlled design.

# 1.4.6 Safety margin calculations, dose selection, dose escalation, and stopping criteria

The optimal dose of clonazepam to restore the excitation/inhibition imbalance is not known. The dose used pre-clinically (0.0625 mg/kg) [11] is comparable to the doses used in mouse seizures models (0.08-0.5 mg/kg). The HED is 0.0625 mg/kg \* scaling factor 0.08 = 0.005 mg/kg, thus 0.35 mg for an adult male, in the same order as the regular starting dose (0.5 mg twice daily), but much lower than the regular maintenance dose (4-8 mg/day). Although generally considered safe, paradoxical reactions have been described in children and elderly. Usually these occur at higher doses. Other reported side effects include dizziness and drowsiness, which are also dose-related. Tolerance usually develops in 1-2 weeks [22, 23].

The dose used in this study is based on the following rationale:

- 1. The pre-clinically effective dose is similar to the starting dose in preclinical seizure models, and the human equivalent dose is in the range of the recommended starting dose for seizures in humans.
- 2. The dose is identical to the dose given to the case of the 12 year old ARID1B patient currently on clonazepam with good clinical effect and absence of toxicity.
- 3. Clonazepam is a registered drug. The recommended starting dose is the same as given in this study.

Therefore, the patients will receive a single starting dose at their first visit of 0.005 mg/kg (max 0.5 mg). Patients will be monitored for 5 hours for safety, PK, and biomarker effect. If the dose on day 1 is well tolerated, patients will take the same dose before bedtime, and continue this regimen as described.

After three days, the (adverse) effects will be evaluated by phone. If the dose on day 1 is well tolerated, the dose will be increased to 0.01 mg/kg/day. After another three days, the effects will be evaluated again, after which the dose will be increased to 0.015 mg/kg/day. During these dosing adjustments, the maximum dose will not exceed 0.5 mg, twice daily. In case of relevant adverse events during any of the dose evaluations, the daily dose will be halved. Then, after three days without relevant adverse events, the dose will be increased to the dose that was prescribed at the time adverse events appeared. When relevant adverse events re-appear, subjects will continue at the lowest tolerable dose.

At the end of the study period, clonazepam will be tapered by decreasing the daily dose by 0.01 mg/kg/day every three days.

## Stopping criteria

Dosing will be stopped in case of an unacceptable tolerability profile based on the nature, frequency, and intensity of observed AEs judged by the investigators.

## 1.4.7 Treatment duration

Since clonazepam has been shown safe and effective in children, and treatment of ARID1B-related intellectual disability would require chronic administration, we have chosen a multiple-dose trial design. The choice for the duration of treatment is based partly on practical considerations and on data on the development of tolerance. It is known that tolerance to different effects of benzodiazepines develops on different time scales. Development of tolerance for sedative effects of benzodiazepines varies from 7 days to 2 weeks in most studies [22, 23], whilst development of tolerance to anti-epileptic

and anxiolytic effects needs much more time to develop. Therefore, we have chosen to treat patients for 3 weeks, to ensure we can establish the effects of clonazepam in absence of the potential sedative side-effects

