## Part B:

The following substances will be administered:

- Active medication. Clonazepam (Rivotril) droplets for oral use, solution 2.5 mg/ml, dissolved in lemonade, tea or juice.
- Placebo: dissolved in lemonade, tea or juice

Study drug or placebo during part B will be administered to the subjects as follows:

- Day 1-3: Starting dose is 0.005 mg/kg, twice daily (max 0.5 mg, twice daily)
- Day 4-6: 0.01 mg/kg, twice daily (max 0.5 mg, twice daily)
- Day 7-22: 0.015 mg/kg, twice daily (max 0.5 mg, twice daily)

Patients will receive a single starting dose at their first visit of 0.005 mg/kg (max 0.5 mg). Patients will be monitored for 5 hours for safety, PK, and biomarker effect. If the dose on day 1 is well tolerated, patients will take the same dose before bedtime, and continue this regimen as described.

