## 7.3 Questionnaire assessments

The Dutch translation of the Aberrant Behaviour Checklist (ABC) will be used [24]. The ABC is a validated questionnaire used for patients with intellectual disability. It consists of 58 symptoms of which the severity of symptoms during the last 2 weeks is scored by parents on a scale of 0-3 (0 = no problem, 3 = the problem is very severe). Parents of ARID1B subjects will complete the questionnaire on day 1 and day 22 of the two treatment periods. Teachers or primary caregivers (in the case of institutionalized care) will complete the questionnaire at the earliest opportunity after day 1 and day 22.

The Clinician Global Impression Score (CGI) is a well-validated clinician-rated measure commonly used in drug studies because it allows the clinician to integrate all sources of information, including the parent/caregiver history, observations in the clinic, and reports from other sources, into a single rating of severity (CGI-S) and improvement (CGI-I) during treatment. The CGI-S will be assessed on day 1 of every treatment period.

For this assessment, the investigator considers all aspects of the subject's neurobehavioral function, including but not limited to internalizing problems, externalizing problems, and social engagement, and rates a scale employing a 7-point Likert scale. The CGI-I monitors improvement and is scored on a 7-point Likert scale: very much improved, much improved, minimally improved, no change, minimally worse, much worse, very much worse. The score will be determined via a semi-structured interview with parents on day 22 of both treatment periods. Furthermore, an additional score will be

determined via a semi-structured phone interview with teachers or primary caregivers at the earliest opportunity after day 22 of both treatment periods.

Conversations made for the CGI assessment will be recorded for review by an independent physician.

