## 7.4 Pharmacodynamic assessments

## 7.4.1 Saccadic eye movements

Saccadic peak velocity is one of the most sensitive parameters for measuring sedation. Recording of eye movements will be performed in a quiet room with dimmed illumination. There will be only one subject per session in the same room. Recording and analysis of saccadic eye movements is conducted with a microcomputer-based system for sampling and analysis of eye movements. The program for signal collection and the AD-converter from Cambridge Electronic Design (CED Ltd, Cambridge, UK), the amplification by Grass (Grass-Telefactor, An Astro-Med, Inc. Product Group, Braintree, Massachusetts, US) and the sampling and analysis scripts have been developed at CHDR (Leiden, the Netherlands). Disposable silver-silver chloride electrodes (Ambu Blue Sensor N) will be applied on the forehead and beside the lateral canthi of both eyes of the subject for registration of the electro-oculographic signals. Skin resistance is reduced to less than 5 kOhm before measurements. Head movements are restrained using a fixed head support. The target consists of a moving dot that is displayed on a computer screen. This screen is fixed at 58 cm in front of the head support. Saccadic eye movements are recorded for stimulus amplitudes of approximately 15 degrees to either side. Fifteen saccades are recorded with interstimulus intervals varying randomly between 3 and 6 seconds. Average values of saccadic peak velocity (expressed as degrees/second) of all correct saccades will be used as parameter and recorded. The measurements of saccadic eye movements will take approximately 3 min.

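### Section 1.4.7 says three weeks of treatment ensures effects are seen without sedation, but the Day 22 ABC looks back over Days 8-21 and can include days before tolerance is expected

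*Protocol*

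**What the plan says.** - **Duration and its purpose.** Section 1.4.7 states: "Development of tolerance for sedative effects of benzodiazepines varies from 7 days to 2 weeks in most studies". It concludes that patients are treated for 3 weeks "to ensure we can establish the effects of clonazepam in absence of the potential sedative side-effects". It mentions neither the dose steps nor the questionnaire recall period.
- **Tolerance and dose.** Section 1.4.6 gives the same range, "Tolerance usually develops in 1-2 weeks", directly after "Other reported side effects include dizziness and drowsiness, which are also dose-related".
- **Dose steps.** The Part B list in Section 5.1 begins with "Day 1-3: Starting dose is 0.005 mg/kg, twice daily (max 0.5 mg, twice daily"), moves to a second step on Days 4-6, and ends with "Day 7-22: 0.015 mg/kg, twice daily (max 0.5 mg, twice daily"). Sections 1.4.6 and 5.2 allow the dose to be halved for adverse events and restored after three event-free days.
- **Endpoints for the multiple-dose objective.** Section 2 names the ABC and the CGI-I. Section 7.3 says of the ABC: "severity of symptoms during the last 2 weeks is scored by parents on a scale of 0-3". Parents complete it on Days 1 and 22. The CGI-I is rated from an interview on Day 22 and has no stated look-back period. It is described as improvement during treatment.
- **Analysis.** Section 9.9.2 compares the ABC change and the CGI-I by paired t-test.
- **Sedation measure.** Section 7.4.1: "Saccadic peak velocity is one of the most sensitive parameters for measuring sedation".

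**The concern.** The argument in Section 1.4.7 sets a 22-day period against a tolerance time of at most 14 days. That comparison suits a measurement reflecting Day 22 alone. The ABC reflects the two weeks before Day 22, and the dose is still rising in the first week. If drowsiness depends on dose, as Section 1.4.6 says, tolerance to the first dose step need not cover the later ones.

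What is at stake is the interpretation of an ABC difference. The subscales listed in Section 6.3 include irritability, social withdrawal and hyperactivity, and sedation could plausibly move parents' ratings of these. The placebo comparison does not remove this, because drug-induced sedation occurs only on active treatment. A reader who relies on Section 1.4.7 would take an ABC benefit as non-sedative, and the protocol's own dates do not secure that.

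**Working it through.** **Inputs**
- Tolerance time L: 7 to 14 days (Sections 1.4.6 and 1.4.7); 10 days is used as an intermediate value.
- Day S from which tolerance is counted: not stated. Tried as Day 1 (first dose), Day 4 (second step) and Day 7 (last step), from the Part B list in Section 5.1.
- ABC window: the 14 days before Day 22, that is Days 8-21 (Section 7.3, parent form).

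**Step 1: the plan's own argument.** Sedation is expected from Day S to Day S + L - 1. The last such day is:
- S = 1: Day 7 (L = 7) to Day 14 (L = 14)
- S = 4: Day 10 to Day 17
- S = 7: Day 13 to Day 20

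Day 22 is later in every case. The 3-week argument therefore reproduces for what is measured on Day 22 itself.

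**Step 2: the ABC window.** For S up to 8, the number of recalled days before tolerance is (S + L - 1) - 8 + 1 = S + L - 8.

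| Counted from | L = 7 | L = 10 | L = 14 |
|---|---|---|---|
| Day 1 | 0 of 14 (0%) | 3 of 14 (21%) | 7 of 14 (50%) |
| Day 4 | 3 of 14 (21%) | 6 of 14 (43%) | 10 of 14 (71%) |
| Day 7 | 6 of 14 (43%) | 9 of 14 (64%) | 13 of 14 (93%) |

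If the window is read as Days 9-22, each non-zero count falls by one; counted from Day 7 it becomes 5, 8 and 12.

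**Step 3: when is more than half the window affected?** This needs S + L - 8 > 7, so L > 15 - S:
- S = 7: L of 9 days or more
- S = 4: L of 12 days or more
- S = 1: L of 15 days or more, outside the stated range

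**Step 4: delayed titration.** If one halving postpones the last step by three days, S = 10. For L = 7 the affected days are 10-16, which is 7 of 14. For L = 14 the expected sedation runs over Days 10-23, so 12 of 14 recalled days are affected and Day 22 itself falls inside.

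**Step 5: which patients have a step on Day 7.** On the twice-daily list, 0.01 mg/kg reaches the 0.5 mg cap at 0.5 / 0.01 = 50 kg. Patients of 50 kg or more are therefore at the cap from Day 4 and have no increase on Day 7. The titration text in Sections 1.4.6 and 5.2 gives the same step figures per day instead. Twice 0.005 is already 0.01 mg/kg/day, so on that wording the second step is no increase. The two wordings must be reconciled. Until they are, it is unclear which row of the table applies to which patient.

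**The case against.** **The claim is right for Day 22.** A patient titrated without delay and stepping up on Day 7 has 15 days (Days 7-21) at that dose before Day 22, against an upper limit of 14. This stands, and the Day 22 NeuroCart tests are not in question.

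**A reader might infer that the ABC largely scores sedated weeks.** The documents do not support that. It needs tolerance to restart at a dose step and to take at least 9 days (Day 7) or 12 days (Day 4). Counted from first dose, the share never exceeds half.

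**A reader might extend the point equally to the CGI-I.** Section 7.3 gives the two-week recall only for the ABC, and Section 6.3 places the CGI-I at the end of the period. No share can be calculated. What remains is that the rating draws on parents' history during treatment and is not shown to be confined to later days.

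**A reader might infer that no patient has more than 15 days at full dose before Day 22.** On the twice-daily list, patients of 50 kg or more have 18 (Days 4-21).

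**The direction of any bias is not established.** Section 1.4.1 lists fatigue, but also irritability and agitation as rare paradoxical reactions. This stands. The point is that a difference cannot be attributed, not that it is inflated.

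**The study is exploratory, and sensitivity analyses may be in a SAP not shown.** Both are fair and limit the weight of the point. Neither repairs a property that the protocol states as ensured.

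**Conclusion.** The point holds as a correction to Section 1.4.7, chiefly for the ABC. Between 0 and 13 of the 14 recalled days may precede expected tolerance: 0-7 counted from first dose, 3-10 from Day 4, 6-13 from Day 7. The stated property is met for the whole ABC window only if tolerance counts from the first, lowest dose and takes 7 days.

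This rests on the protocol's own 7-14 day range, a window of Days 8-21, undelayed titration, and treating sedation as present until the tolerance day and absent afterwards. That last assumption is a simplification, so the counts are days at risk and not a measured amount of sedation. For the CGI-I the conclusion is only that freedom from sedation is not shown.

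**What to change.** 1. **In Section 1.4.7**, limit the claim to tests performed on Day 22 in patients whose titration was not delayed. State that an ABC difference, and possibly a CGI-I difference, may partly reflect sedation and will not be described as non-sedative on the basis of treatment duration alone.
2. **Report beside the ABC and CGI-I results** the sedation-relevant data already collected. These are the active-minus-placebo difference in Day 22 pre-dose saccadic peak velocity, and the Day 2-21 home tests, activity, sleep and adverse events. Label the saccadic result as residual sedation on Day 22 only.
3. **Reconcile** the per-administration and per-day dose wording in Sections 1.4.6, 5.1 and 5.2 and the synopsis.

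Three further steps may look attractive but are not recommended:
- **A saccadic threshold as a gate for the ABC claim.** Day 22 velocity cannot show what happened on Days 8-20, and the 13.95 degrees/s in Section 1.4.9 is a minimum detectable effect, not a sedation margin.
- **Adjusting the ABC for the saccadic difference.** This conditions on a post-treatment variable and is open to bias.
- **A 7-day recall (Days 15-21).** Counted from Day 7, it still leaves 0-6 of 7 days affected and departs from the stated recall period.

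The cost is a few sentences and some descriptive comparisons on existing data, with no new assessments. The price is more cautious wording of a positive ABC or CGI-I result.
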